7.1.3 Per-protocol analysis set / Per-protocol analysis

The Per-Protocol analysis (PP analysis) will be based on data from all subjects in the FAS not affected by major protocol deviations. Major protocol deviations are defined as protocol deviations that impact the assessment of the primary/secondary endpoints.

The Per-protocol Set (PPS) comprises all subjects included in the FAS without any major protocol deviations occurring prior to or at randomization. Due to the nature of the primary endpoint which is assessed over the entire study period rather than at a fixed time point, for subjects developing major protocol deviations during the study, only data collected after a major protocol deviation will be excluded from the PP analysis.

Subjects will be excluded from the PPS if:

- **Subject is randomized and did not satisfy certain eligibility criteria:**

- Subject presenting no diagnosis of MS as defined by the revised (2010) McDonald Diagnostic Criteria for MS or with no relapsing course from onset (no diagnosis of RRMS or SPMS with superimposed relapses) [PD_PP.013];
- No active disease as required per study protocol inclusion criterion 5 [PD_PP.014];
- Diagnosis of MS with progressive course from onset (i.e., diagnosis of primary progressive MS or progressive relapsing MS) [PD_PP.047];
- Treatment within 90 days prior to randomization with medication listed in study protocol exclusion criterion 8 [PD_PP.024], medications: Plasmapheresis, cytapheresis, i.v. immunoglobulin, Treatment with an investigational drug (within 90 days or five half-lives of the drug, whichever is longer), except biological agents;
- Treatment within 180 days prior to randomization with medication listed in study protocol exclusion criterion 9 [PD_PP.025], medications: Azathioprine, methotrexate, or cyclophosphamide, Natalizumab, Other systemic immunosuppressive treatment (e.g., cyclosporine, sirolimus, mycophenolic acid), Non-lymphocyte-depleting experimental biological agents (e.g., daclizumab);
- Treatment within 24 months prior to randomization with lymphocyte-depleting biological agents (e.g. rituximab or ocrelizumab) or cladribine [PD_PP.026];
- Treatment at any time prior to randomization with alemtuzumab, mitoxantrone, leflunomide, teriflunomide, fingolimod, ponesimod or other investigational S1P modulators, stem-cell transplantation [PD_PP.027];

- **Subject received no treatment or did not comply with treatment:**

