- No treatment taken: Any randomized subject who never received study drug [PD_MM.175] is excluded from the Per Protocol Set;
- Compliance < 80 %, as per compliance based on days on study drug, derived from the eCRF, as described in Section 5.3.2.1, is excluded from the Per Protocol Set

Data will be excluded from the per protocol analysis for subjects after the occurrence of one of the following criteria:

- **Subject received wrong study treatment or incorrect dose:**

- Wrong study treatment taken for > 14 days (> 2 consecutive kits as one kit contains 7 doses): Derived as protocol deviation ‘Study drug taken from a non-allocated kit’ [PD_MM.058] and only applies if at least 2 non-allocated kits containing wrong treatment (derived at unblinding: PD_MM.0581) have been taken, exclusion from first intake start date + 14 days onwards. *Note: Wrong study*

treatment taken for ≤ 14 days is not expected to affect efficacy considerably based on pharmacodynamic profile of the study treatment.

- Premature treatment discontinuation: Any randomized subject with premature treatment discontinuation, derived from the eCRF, as described in Section 5.1.5, exclusion from EOT + 7 days onwards.
- **Subject took an unauthorized concomitant medication:**
 - Treatment with systemic corticosteroids and ACTH during treatment, except for MS relapses and short-term treatments with low dose/inhaled corticosteroids for pulmonary conditions defined in study protocol [PD_MM.087], from date of protocol deviation onwards;
 - Any administration of disease modifying therapy for MS during the treatment period [PD_MM.088, PD_MM.093], exclusion from medication start date onwards;
 - During treatment period, any investigational procedure for MS [PD_MM.096], from date of procedure onwards;
- **Occurrence of major protocol deviation that could confound the interpretation of analysis conducted on the FAS;**
 - EDSS assessments not conducted for more than 6 months, exclusion from ‘last EDSS date prior to 6-month gap + 6 months’ onward; derived from eCRF: time between two consecutive EDSS assessments (or last EDSS assessment and EOS date) is > 6 months (182 days).
 - Subject’s randomized treatment allocation was unblinded. Treatment code broken before unblinding of the study (for a reason not related to management of a clinical event [PD_MM.054], or any other unblinding documented in the IRT/eCRF), exclusion from date of unblinding onwards.

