9.6.5.2 ARR based on confirmed relapses up to EOS - Per protocol analysis

Same analysis as for the main analysis, but with number of confirmed relapses up to EOS (per-protocol) as a response variable and the logarithm of time (in years) between randomization and EOS (or up to per protocol exclusion date) as an offset variable based on the PPS. Conducted to check the consistency of the treatment effect in the per protocol analysis with the effect in the main analysis. This analysis will evaluate whether a bias in evaluating the treatment effect has been introduced in the FAS due to major protocol deviations.

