9.6.6.2 Number of new or worsening neurological symptoms up to EOS

New or worsening neurological symptoms up to EOS are summarized overall and by sub-categories (confirmed relapse, non-confirmed relapse, symptoms not considered a relapse) using descriptive statistics by treatment arm. Percentages for sub-categories are presented out of the total number of new or worsening neurological symptoms.

New or worsening neurological symptoms are reported via a telephone interview or at the site in a face-to-face interview and at both these times a decision must be taken by the treating neurologist to refer the subject to the efficacy assessor. Once referred to the efficacy assessor the symptom is considered a relapse and is assessed for confirmation. To ensure there is no bias in the selection of symptoms considered as relapses between treatments, an analysis will compare the proportion of these new or worsening neurological symptoms that are considered as relapses or as confirmed relapses. If there is an imbalance in the selection between treatments, this will be explored further.

9.6.6.3 Change in the collection of the primary endpoint introduced by protocol amendment 3

To investigate the impact of protocol amendment 3, the cumulative time in the study with data collected under protocol version 3 or earlier (prior to switching to PV4) as a proportion of the total cumulative time in the study will be calculated. Depending on the proportion of data collected under each protocol, further supportive analysis will be introduced to assess the impact of the change in the method of the primary endpoint collection. The analysis is detailed in Section [9.3.1](#).

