2.5. Blinding

Condition	Type	Identifier	Source/Instructions	Additional information expected?	Important PD
At least one Actelion study team member (except site monitor, CCMM, FDM, first dose data scientist) had access to data potentially revealing treatment assignment as defined in study protocol	M	PD_MM.052	CTT PD / Except alerts as defined per study protocol		Yes
PI/study nurse or any other personnel involved in clinical care and management of subject deliberately tried to find out treatment assignment	M	PD_MM.053	Monitor PD / e.g., local lab results of lymphocytes		Yes
Any MRI report containing MS-related information without justification documented on the report	M	PD_MM.154	Monitor PD / Except in case of pre-defined threshold documented at site		No
Treatment code broken before unblinding of the study for a reason not related to management of a clinical event	M	PD_MM.054	eCRF / Monitor PD / Date of unblinding as per IxRS + GDS	Date of unblinding	Yes
Efficacy assessor involved in clinical care and management or made aware of any data potentially revealing treatment assignment	M	PD_MM.050	Monitor PD / e.g., AEs, ECGs, Lab results; Monitor to provide date of potential unblinding	Date of potential unblinding	Yes
Any site personnel involved in clinical care and management of subject who have had a potential access to day 1 or re-initiation data	M	PD_MM.051	Monitor PD / Monitor to provide date of potential unblinding	Date of potential unblinding	No
Any site personnel made aware of any data with unblinding potential assessed as high or moderate not related to management of a clinical event (except day 1 or day of re-initiation of study drug data)	M	PD_MM.152	Monitor PD / Data reviewed by at least one site member (except alerts as defined per protocol) or broken capsules in more than one patient at one site. Monitor to provide date. Unblinding type to be provided to CDDM based on "Potential Unblinding Event Documentation Form"); Type of unblinding to be reported for BST only for lymphocytes and/or WBC	Date of potential unblinding\ Type: Lymphocytes\ WBC	Yes

	TPL-100062 Protocol Deviation Code List
Protocol Number: AC-058B301 Acronym: OPTIMUM	

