Any site personnel made aware of data with unblinding potential assessed as low (except day 1 or day of re-initiation of study drug data)	M	PD_MM.202	Monitor PD / Data received but site claiming not reviewing the results (except alerts as defined per protocol) or single broken capsule; Monitor to provide date. Unblinding type to be provided to CDDM based on "Potential Unblinding Event Documentation Form"); Type of unblinding to be reported for BST only for lymphocytes and/or WBC	Date of potential unblinding \ Type: Lymphocytes \ WBC	No
Any site personnel involved in clinical care and management of subject who has reviewed Day 1 or re-initiation data	M	PD_MM.203	Monitor PD / Monitor to provide date of unblinding	Date of potential unblinding	Yes

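### The per-protocol blinding criterion in SAP 7.1.3 omits PD_MM.050, so the per-protocol analysis does not test for bias from functional unblinding of the efficacy assessor

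*SAP*

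**What the plan says.** SAP 7.1.3 gives the test for what counts: "Major protocol deviations are defined as protocol deviations that impact the assessment of the primary/secondary endpoints". For subjects who develop such a deviation during the study, only the data collected afterwards are dropped.

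The one blinding item in the list of data cuts sits under deviations that could confound the full-analysis-set result, and concerns a subject whose allocation was unblinded. It has two limbs: "Treatment code broken before unblinding of the study (for a reason not related to management of a clinical event [PD_MM.054"], and then "or any other unblinding documented in the IRT/eCRF), exclusion from date of unblinding onwards".

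Section 9.6.5.2 gives the purpose of the per-protocol ARR analysis: "This analysis will evaluate whether a bias in evaluating the treatment effect has been introduced in the FAS due to major protocol deviations".

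The Protocol Deviation Code List attached to the SAP (section 2.5, Blinding) defines several further events. PD_MM.050 reads "Efficacy assessor involved in clinical care and management or made aware of any data potentially revealing treatment assignment", with the instruction "Monitor to provide date of potential unblinding". PD_MM.203 reads "Any site personnel involved in clinical care and management of subject who has reviewed Day 1 or re-initiation data". PD_MM.152 covers site personnel who learn of data with high or moderate unblinding potential, and PD_MM.053 covers deliberate attempts by the treating team to learn the assignment. None of the four is named in 7.1.3.

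**The concern.** The SAP treats functional unblinding as a live risk. Section 2.1.2 keeps first-dose and re-initiation adverse events, hourly vital signs and ECGs, and all post-baseline lymphocyte and white-cell data, away from the sponsor's trial team because they may reveal treatment.

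The endpoints at risk rest on judgement. Section 5.4.1 defines the primary endpoint by relapses confirmed according to the treating neurologist or principal investigator. Section 9.6.6.2 describes the efficacy assessor's part: "Once referred to the efficacy assessor the symptom is considered a relapse and is assessed for confirmation". CDA rests on the reported EDSS score (5.4.2.3.1), and code PD_MM.160 shows that the efficacy assessor is expected to perform EDSS components.

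An assessor who has seen revealing data could rate relapses or EDSS differently by arm. If those ratings stay in the per-protocol analysis, a reader who takes its agreement with the main analysis as evidence against bias from deviations would be reassured on a point that was never tested.

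**Working it through.** No arithmetic settles this. The check sets the 7.1.3 criterion beside the code list, section 2.5.

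| Code | Event | Important | Source | Date collected | Named in 7.1.3 |
|---|---|---|---|---|---|
| PD_MM.054 | Code broken, not for clinical management | Yes | eCRF / Monitor PD | Yes, date of unblinding | Yes |
| PD_MM.050 | Efficacy assessor in care, or aware of potentially revealing data | Yes | Monitor PD | Yes, potential unblinding | No |
| PD_MM.152 | Site personnel aware of high/moderate-potential data | Yes | Monitor PD | Yes, potential unblinding | No |
| PD_MM.203 | Treating personnel reviewed Day 1 or re-initiation data | Yes | Monitor PD | Yes, potential unblinding | No |
| PD_MM.053 | Deliberate attempt to learn assignment | Yes | Monitor PD | None listed | No |

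1. *Does the second limb of 7.1.3 reach these codes?* On its wording it requires unblinding recorded in the IRT or eCRF. The code list separates eCRF from Monitor PD as sources, and the last four rows list Monitor PD alone. They are caught only if the same event also happens to be recorded as unblinding in the IRT or eCRF.

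2. *Does PD_MM.050 meet the 7.1.3 definition of a major deviation?* It concerns the person who assesses relapses for confirmation and takes part in EDSS rating. Loss of that person's independence bears on assessment of the primary endpoint and both CDA endpoints. This follows from what the code describes, not from its Important flag.

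3. *Do other planned analyses cover the gap?*
   - 9.6.5.3 repeats ARR on all relapses, as a check on confirmation.
   - 9.6.6.2 compares arms on the share of reported symptoms taken as relapses or confirmed relapses, as a check on selection. It uses the questionnaire that began with protocol version 4 (5.4.1.2.9).
   - 9.3.2 tabulates deviations by high-level topic and arm, without an effect estimate.
   - The supportive CDA analyses (9.7.3.3 for 12 weeks; 9.7.1.4 in the 24-week section) include none for unblinding, and their per-protocol versions inherit the 7.1.3 rule.

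   None isolates subjects with a blinding deviation, and none covers EDSS.

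4. *Illustration for one hypothetical subject.* Assume a PD_MM.050 event at Week 12 and no other cut before Week 108. Follow-up kept in the per-protocol analysis after the event is 108 − 12 = 96 weeks, and 96/108 = 0.889, or about 89%. This shows how the rule works; it says nothing about the effect on ARR or CDA.

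**The case against.** The strongest case for the existing rule is that it cuts on unblinding, whereas the other codes record only potential unblinding. PD_MM.050 is triggered by mere involvement in care, or by awareness of an adverse event or laboratory result. PD_MM.152 covers any site personnel and includes broken capsules in more than one patient at a site. PD_MM.053 records an attempt, not a success. This stands, and it is why the broader codes do not belong in the per-protocol definition.

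Cutting at these dates could also introduce bias. Section 2.1.1 attributes the first-dose effect to ponesimod, so revealing events may cluster in one arm and follow-up may be removed unevenly. This stands as a limit on interpretation.

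Important is not the same as major: the flag also covers late SAE reporting (PD_MM.105) and contraception lapses (PD_MM.081). That is correct, but the case for PD_MM.050 rests on its content.

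Some stronger readings are tempting and are not supported. A reader might infer that data are removed only after a formal code break; the second limb is wider, covering any other unblinding documented in the IRT or eCRF. A reader might also infer that the plan never looks for biased relapse ascertainment; 9.6.5.3 and 9.6.6.2 do, though indirectly. Nor does the SAP designate the per-protocol analysis as its test for assessor unblinding: 9.6.5.2 speaks of major deviations in general. The point is that a deviation meeting the SAP's own description of major is left out of it.

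**Conclusion.** The gap is real but confined to supplementary analyses. The per-protocol analysis removes data only after unblinding of allocation documented in the IRT or eCRF. It keeps assessments made after an efficacy assessor became aware of potentially revealing data, so it does not test for bias from functional unblinding. For relapses, indirect checks exist elsewhere; for 12- and 24-week CDA there is none.

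The size of any bias cannot be judged, because the SAP gives no count of these deviations by arm or overall. It would be wrong to infer that the primary result is biased: the main analyses of the primary and secondary endpoints use the full analysis set (7.1.2) and do not depend on this rule.

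The conclusion assumes that Monitor PD entries are not also recorded as unblinding in the IRT or eCRF, and that the efficacy assessor's role is as 9.6.6.2 and the code list describe. The change is worth making because the codes and dates needed for it are already collected.

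**What to change.** 1. In 7.1.3, add PD_MM.050 to the data-exclusion criteria, with data excluded from its recorded date onwards. The per-protocol variables in 5.4.1.2.4, 5.4.2.3.2.1 and 5.4.2.4.2.1 refer back to 7.1.3, so the change carries through to ARR and both CDA endpoints.

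2. Prespecify one supplementary analysis of ARR and 12- and 24-week CDA on the full analysis set, censoring each subject at the first PD_MM.050, .152 or .203 date, and report the number of affected subjects by arm.

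3. List PD_MM.053 by subject and arm, but do not use it as a cut: it has no date field and records only an attempt.

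The cost is SAP wording and one additional set of outputs; no new data collection is needed. The drawbacks are less data in the supplementary analyses and possible arm-differential censoring. Both should be stated alongside the results, with the counts by arm as the first thing to read.

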7.1.4 Safety analysis set

The safety analysis set (SAF) includes all subjects who received at least one dose of study treatment. Irrespective of the randomized treatment group, subjects are summarized grouped:

- by actual treatment received, if the same kind of study treatment (teriflunomide or ponesimod) was taken throughout the study.
- within the treatment group they were exposed to for the majority of time on study treatment in case both study treatments (teriflunomide and ponesimod) were taken by a subject at some point during the study. If a subject received teriflunomide and ponesimod for exactly the same number of days, they are summarized within the treatment they are assigned to by randomization.

Some analyses are conducted based on the following safety set subsets:

- Subset of subjects with at least one re-initiation (based on eCRF Study Drug Administration - Re-Initiation)
- Subset excluding subjects from centers in Canada, the United States, and Mexico. Subset is used to address differences in assessment schedule of laboratory assessments in local protocol versions as compared to the global protocol version.
- Subset of subjects who received non-randomized study drug during the study (derived from protocol deviation PD_MM.058.1)
- Subset of subjects who resumed ponesimod maintenance treatment without up-titration after an interruption of >3 days [see Section 5.3.2.2]
- Subset of subjects who deviated from planned up-titration regimen [see Section 5.3.2.2]

7.1.5 Other analysis sets

The following other analysis sets are defined:

7.1.5.1 *Non-conventional MRI sub-study full analysis set*

Includes all subjects in the full analysis set who have consented to participate in the non-conventional MRI techniques sub-study ('Non-conventional MRI techniques sub-study' ticked on 'Informed Consent' eCRF).

7.1.5.2 *Patient preference sub-study full analysis set*

Includes all subjects in the full analysis set who have consented to participate in the Patient Preference sub-study ('Patient Preference Questionnaire' ticked on 'Informed Consent' eCRF).

7.1.5.3 *DL_{CO} sub-study safety analysis set*

Includes all subjects in the safety set who have consented to participate in the DL_{CO} sub-study ('DL_{CO} sub-study' ticked on 'Informed Consent' eCRF). Subjects are summarized in the same treatment group as in the safety analysis set.

7.1.5.4 *Post-treatment observation period analysis set (PTOP Set)*

Includes all subjects in the full analysis set who prematurely discontinued treatment (see definition in Section 5.1.5), with EOS date after EOT + 7 days.

7.1.5.5 *Post-treatment safety analysis set*

Includes all subjects in the safety analysis set who have an EOS date > EOT + 15 days. Subjects are summarized in the same treatment group as in the safety analysis set.

7.2 Usage of the analysis sets

Table 7 provides an overview of the analysis set usage for the main variables of the study.

Table 7 Overview of the different main analysis sets and their usage

Analyses/Data Displays	Screened analysis set	Full analysis set	Safety analysis set	Per protocol analysis set
Inclusion/exclusion criteria	✓			
Demographic characteristics		✓		✓
Baseline characteristics		✓		✓
Medical history		✓		
Previous and concomitant medications		✓		
Treatment exposure			✓	
Efficacy: Primary endpoint		✓		✓
Efficacy: Secondary endpoints		✓		✓
Efficacy: Exploratory endpoints		✓		
Safety endpoints			✓	
All subject listings		✓		

Main analysis of the primary efficacy endpoint is based on the Full analysis set, selected listings will be prepared on the Screened analysis set.

8 DEFINITION OF SUBGROUPS

The below described subgroups are considered in selected efficacy analyses. If applicable, the category in bold type is the reference category used in the statistical analysis of these subgroups.

- Prior use of MS disease-modifying treatment in the last two years prior to randomization (yes, **no**) as documented by the IRT system and used as randomization strata.
- Baseline Expanded Disability Status Scale score (**EDSS ≤ 3.5**, EDSS > 3.5) as documented by the IRT system and used as randomization strata.
- Prior use of MS disease-modifying treatment in the last two years prior to randomization (yes, **no**) as derived based on medications entered in the eCRF [see Section 5.2.2].
- Any prior treatment for MS (yes, **no**).
- Baseline Expanded Disability Status Scale score (**EDSS ≤ 3.5**, EDSS > 3.5) as documented in the eCRF.
- Geographical region of site (Europe Non-EU + Russia, European Union (EU) + UK, North America, Rest of World), as defined in Section 5.2.1;
- Sex (**male**, female);
- Age at screening (< **40 years**, ≥ 40 years);
- MS subtype (**relapsing remitting**, secondary progressive with superimposed relapses)

- Number of documented MS relapses within the last 12 months prior to screening (≤ 1 , ≥ 2), as defined in Section 5.2.2;
- Gd+ T1 lesions at baseline, on MRI scan as provided by the central reader (**absent**, **present**);
- Highly active disease (yes, **no**), as defined in Section 5.2.2;
- Protocol version at randomization:
 - **Randomized pre-PV4**: Subjects who have consented originally to protocol versions 1 to 3; these subjects can have data collected under protocol versions 1 to 3 only or under protocol versions 1 to 4.
 - **Randomized post-PV4**: Subjects who have consented to PV4 only; data of these subjects is only being collected under PV4.derived as described in Section 5.1.8.

In case of missing information, the corresponding subject is not considered for the respective subgroup analysis.

